5.1 Dose Modification

Dose Level mg BID	INCB018424 (Days 1-21 Q 4 weeks)	Lenalidomide QD
Dose Level +3	25	15
Dose Level +2	20	10
Dose Level +1	20	5
Level 0	15	5
Dose Level -1	10	5
Dose Level -2	10	5 mg every other day x 10
Dose Level -3	5	5 mg every other day X 10

If drug-related grade 3 or 4 non-hematologic toxicity is attributable to one or both of the drugs, dose interruption of that particular drug(s) is mandatory. Patient who experience grade 3 drug related non-hematological toxicity may be given a subsequent course one dose level below the previous course, but the patient must have recovered to grade ≤ 1 before institution of the next course. If a patient has drug-related grade 4 non-hematologic toxicity, he/she may receive a subsequent courses at one reduced dose level after resolution of toxicity to grade ≤ 1 , only if approved by the Principal Investigator based on the clinical significance of the toxicity and only if patient has had derived a benefit from the therapy. The dose of therapeutic agents can be decreased during a cycle, at the discretion of treating physician, for chronic grade 2 non-hematologic toxicity. In specific circumstances, after discussion with the Principal Investigator, one of the two medications can be discontinued for safety. Documentation of the reason(s) study drug is discontinued is required. Other dose modifications may be considered as clinically indicated with documentation and approval of the PI

During a cycle of therapy, dosing of INCB018424 and lenalidomide will be discontinued for platelet counts $\leq 35 \times 10^9/L$ OR for ANC $\leq 500/uL$. Dosing of INCB018424 may resume at 5mg QD if the platelet count increases $> 35 \times 10^9/L$ AND ANC $> 500/uL$, and can be increased to 5mg BID for the remainder of the cycle once platelet count is $> 50 \times 10^9/L$ AND ANC $> 1000/uL$. Lenalidomide will not be restarted during this cycle.

Patients who experience platelet count $\leq 35 \times 10^9/L$ or ANC $\leq 500/uL$ during a cycle of therapy, will have a dose reduction of therapy by one dose level for subsequent

cycles. A reduction of 2 dose levels may be considered if the myelosuppression was deemed severe and life threatening by the treating physician, and if it is in the patient's best interest. Reductions in dosing for therapy related anemia can be done at the discretion of the investigator.

Patients may be escalated to the next higher dose level if ALL of the following criteria are met (for the study drug being dose escalated). (Applicable also for patients receiving only one study drug)

1. no dose reductions due to toxicity were required in the prior 2 cycles
2. no dose interruptions due to toxicity were required in the prior 2 cycles
3. the prior cycle was not delayed due to toxicity
4. the current cycle is not delayed due to toxicity
5. Platelet count $\geq 100 \times 10^9/L$ AND ANC $\geq 1000/uL$
6. The patient has sub-optimal benefit defined as a failure to reduce palpable spleen length by at least 50% and/or suboptimal improvement in MF related symptoms as assessed by the investigator, and/or failure to improve cytopenia
7. no development of new onset transfusion dependency

Dose modifications/discontinuation for prednisone therapy will be at the discretion of the clinician but must be documented clearly when it happens. Prednisone dose modification/discontinuation will not require withdrawal from the study. Treatment of hyperglycemia with either oral hypoglycemic agents or insulin does not necessarily require discontinuation of prednisone if the hyperglycemia is controlled with these medications.

5.2 Initiation of a New Cycle of Therapy

A new course of treatment may begin on the scheduled Day 1 of a new cycle if:

- The ANC is $\geq 1,000/\mu L$;
- The platelet count is $> 50 \times 10^9/L$,
- Any drug-related grade 3-4 adverse event that may have occurred has resolved to \leq grade 1 severity;

If these conditions are not met on Day 1 of a new cycle, the subject will be evaluated weekly and a new cycle will not be initiated until the toxicity has resolved as described above. If drug dosing was interrupted during the previous cycle or if the new cycle is delayed due to toxicity newly encountered on the scheduled Day 1, then the new cycle will be started when the criteria above are met AND with at least a one-level dose reduction. Treatment with INCB018424 may continue at 5mg QD so long as $ANC > 500/uL$ AND platelets $> 35 \times 10^9/L$ or at 5mg BID so long as $ANC \geq 1000/uL$ AND platelets $> 50 \times 10^9/L$ while waiting to initiate a new cycle. If after a 4 week delay, the platelet count remains $> 50 \times 10^9/L$ but $\leq 75 \times 10^9/L$, the next cycle therapy may begin with INCB018424 dosed at 5mg BID and the dose of lenalidomide reduced by at least 1 dose level from the prior cycle. If the prior cycle was at dose level -2 or -3 then lenalidomide (and prednisone if started) must be discontinued and the patient may continue therapy with INCB018424 alone following dosing rules.

If the toxicity has not resolved as described above within 8 weeks of the scheduled start date for the cycle, the patient will discontinue treatment. In unusual circumstances this rule may be modified by the Principal Investigator if felt to be in the best interest of the patient (for example, responding patient with neutropenia or low platelets, that resolve past 6 weeks may be restarted on therapy); this case must be fully documented.

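### The restart dose reduction is not tied to the drug blamed for a non-hematologic toxicity; by the table's rows, the minimum step from Level 0 leaves lenalidomide at 5 mg daily and lowers only INCB018424

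*Combined protocol and SAP*

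**What the plan says.** Section 5.1 is drug-specific about interruption. When a related grade 3 or 4 non-hematologic toxicity is attributed to one or both drugs, "dose interruption of that particular drug(s) is mandatory". It is not drug-specific about restarting. After grade 3, and once the event has recovered to grade 1 or better, the patient "may be given a subsequent course one dose level below the previous course". After grade 4 the same single step is available, but "only if approved by the Principal Investigator based on the clinical significance of the toxicity" and only if the patient has benefited.

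Section 5.2 makes a reduction compulsory if dosing was interrupted in the previous cycle or the new cycle is delayed on Day 1 for toxicity: "then the new cycle will be started when the criteria above are met AND with at least a one-level dose reduction".

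The term dose level is defined only by the Section 5.1 table, in which every level is a pair of doses. Level 0, the starting dose in Section 5.0, is INCB018424 15 mg BID with lenalidomide 5 mg daily. Level -1 is 10 mg BID with lenalidomide 5 mg daily. Lenalidomide first falls at Level -2.

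There is discretion around this default. Section 5.1 says that "one of the two medications can be discontinued for safety" in specific circumstances, and it allows other modifications with PI approval.

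**The concern.** A physician who follows the minimum rule after a grade 3 event blamed on lenalidomide would restart lenalidomide at the dose that preceded the event and reduce a drug that was not blamed. That undercuts the purpose of attributing the event.

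The case is foreseeable. It starts from the planned starting dose, and Section 2.3 lists non-hematologic events reported with lenalidomide (regardless of relationship), among them diarrhea, rash and infections.

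What is at stake is the safety of the restart and consistency between treating physicians. Low counts are a different matter: both drugs are myelosuppressive, and lowering INCB018424 first for cytopenia is defensible.

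**Working it through.** **Inputs.** Doses are from the Section 5.1 table. Section 5.0 gives the schedules: INCB018424 twice daily without a break, lenalidomide on days 1-21 of 28. I take 5 mg every other day x 10 to mean ten doses per cycle.

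**Formulas.** INCB018424 mg/day = 2 × BID dose. Lenalidomide mg/cycle = daily dose × 21, or 5 × 10 = 50 for the every-other-day schedule.

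| Level | INCB018424 mg/day | Lenalidomide mg/cycle |
|---|---|---|
| +3 | 2 × 25 = 50 | 15 × 21 = 315 |
| +2 | 2 × 20 = 40 | 10 × 21 = 210 |
| +1 | 40 | 5 × 21 = 105 |
| 0 | 2 × 15 = 30 | 105 |
| -1 | 2 × 10 = 20 | 105 |
| -2 | 20 | 50 |
| -3 | 2 × 5 = 10 | 50 |

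**Effect of one row down.**

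| Step | INCB018424 | Lenalidomide |
|---|---|---|
| +3 to +2 | -20% | -33% |
| +2 to +1 | 0% | -50% |
| +1 to 0 | -25% | 0% |
| 0 to -1 | (20 - 30)/30 = -33% | 0% |
| -1 to -2 | 0% | (50 - 105)/105 = -52% |
| -2 to -3 | -50% | 0% |

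Six steps and two drugs give 12 combinations. A drug blamed alone is unchanged in 3 (lenalidomide) + 2 (INCB018424) = 5 of 12, so the mismatch runs in both directions. Two of the five (+2 to +1 and +1 to 0) need earlier escalation. From Level 0 downward it is 3 of 6.

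**Three readings of one level down from Level 0, lenalidomide blamed alone.**

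- By row: lenalidomide 105 to 105 mg per cycle; INCB018424 15 to 10 mg BID.
- By the lenalidomide column only: the Level -1 entry is still 5 mg daily, and INCB018424 stays at 15 mg BID. Neither drug falls.
- By distinct lenalidomide dose: 5 mg daily to 5 mg every other day x 10, or 105 to 50 mg per cycle (-52%); INCB018424 unchanged.

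Only the third does what attribution implies, and no row of the table contains that pairing. The first row with less lenalidomide is Level -2, which also lowers INCB018424 to 10 mg BID.

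**The same ambiguity elsewhere.** Section 5.2 has a rule for platelets above 50 but not above 75 × 10⁹/L after a 4-week delay. It asks for "the dose of lenalidomide reduced by at least 1 dose level from the prior cycle". By row, that is 5 mg to 5 mg from Level +1 or Level 0. The next sentence points to distinct doses: "If the prior cycle was at dose level -2 or -3 then lenalidomide (and prednisone if started) must be discontinued". Level -2 has a row below it with the same lenalidomide dose, yet the rule stops the drug there, as if the every-other-day schedule were the last step.

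**The case against.** The strongest reply is that the row reading is not the only one. Section 5.1 limits its escalation criteria by "for the study drug being dose escalated", Section 5.2 speaks of a dose level of lenalidomide on its own in the platelet rule, and interruption is by drug. Someone who reads levels that way throughout would reduce lenalidomide to every other day and leave INCB018424 alone. This stands to the extent that the row reading cannot be presented as the only possible one. But that wording belongs to escalation and to one platelet rule. No separate lenalidomide ladder is given, and reading the existing column by itself still returns 5 mg daily.

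The second reply is that safeguards already exist. The patient must first have recovered to grade 1 or better. The restart is permitted, not compelled, and the minimum can be exceeded. One drug may be stopped, and the PI may approve other changes. Section 5.6 requires the center's approval of dose changes for patients followed locally, and Section 5.7 stops treatment for events that may cause severe or permanent harm. All this softens the consequence. None of it changes the default, and a two-level step from Level 0 lowers both drugs.

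The third reply is that no consequence has been measured. This also stands. The starting lenalidomide dose is half the 10 mg/day of the cited lenalidomide studies (which used 5 mg when platelets were below 100 × 10⁹/L), and the documents give no rate of grade 3 events due to lenalidomide alone at 5 mg. The 5 of 12 counts table cells, not patients.

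A reader might infer that the protocol obliges physicians to re-expose patients to the offending dose. It does not, because lower doses are open to them. A reader might also infer that the response rate or the two-stage error rates are compromised. The documents do not support that: Section 2.2 describes individual titration of INCB018424, 10 mg BID lies within it, and there is no event rate from which to calculate an effect.

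**Conclusion.** The point holds as a minor defect in the dosing rules. Attribution governs which drug is interrupted but not which drug is reduced. On the only dose levels defined, the compulsory minimum from the starting dose can therefore return the patient to an unchanged dose of the blamed drug.

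The conclusion assumes that a level is a row of the table, that the event is attributed to lenalidomide alone, and that the physician takes no more than the minimum step. If the investigators intended levels by drug and by distinct dose, the defect is one of wording and the same clarification settles it. Confidence is medium because of the mixed wording.

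**What to change.** State in Sections 5.1 and 5.2:

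- After grade 3 or 4 non-hematologic toxicity attributed to one study drug, that drug restarts at its next lower distinct dose and the other keeps its dose. Lenalidomide: 15, 10, 5 mg daily on days 1-21, then 5 mg every other day x 10, then stop. INCB018424: 25, 20, 15, 10, 5 mg BID.
- If the toxicity is hematologic, or cannot be attributed to one drug, use the next lower row of the table.
- Keep the recovery condition of grade 1 or better and, for grade 4, the PI-approval and benefit conditions.
- The platelet 50-75 rule uses the distinct lenalidomide doses.
- For a pairing that is not a row, a later low-count reduction lowers INCB018424 by one distinct dose. For example, 15 mg BID with every-other-day lenalidomide goes to Level -2. If INCB018424 is already at 5 mg BID, lower lenalidomide instead: 5 mg BID with 5 mg daily goes to Level -3.

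Leave the escalation rules as they are. Escalating drug by drug through distinct doses would allow lenalidomide 10 or 15 mg with INCB018424 15 mg BID, whereas the table pairs those lenalidomide doses only with 20 mg BID or more.

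**Cost.** The dosing text is slightly longer, with no new dose strength, visit or procedure. Some patients receive pairings not in the table, and escalating from such a pairing would need a PI-approved choice. From Level 0, a second event attributed to lenalidomide leads to stopping it, which Section 8.0 counts as a failure when done for safety. The present table offers three rows below Level 0 before it runs out.

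### Section 5.2 permits INCB018424 to continue on blood counts alone while a cycle is held, which contradicts Section 5.1 when the hold is for a non-hematologic grade 3-4 event attributed to that drug

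*Combined protocol and SAP*

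**What the plan says.** Section 5.2 (Initiation of a New Cycle of Therapy) sets three conditions for starting a cycle on its scheduled Day 1:

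1. ANC of at least 1,000/µL.
2. Platelets above 50 × 10⁹/L.
3. "Any drug-related grade 3-4 adverse event that may have occurred has resolved to" grade 1 or less.

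If any of these fails, the patient is checked weekly and "a new cycle will not be initiated until the toxicity has resolved as described above".

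The same paragraph then gives a bridging permission: "Treatment with INCB018424 may continue at 5mg QD so long as" ANC is above 500/µL and platelets are above 35 × 10⁹/L. It also allows 5 mg BID when ANC is at least 1,000/µL and platelets are above 50 × 10⁹/L. Both branches apply "while waiting to initiate a new cycle". The sentence does not mention why the cycle is held, what kind of event is involved, or which drug it is attributed to.

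Section 5.1 (Dose Modification) deals with drug-related grade 3 or 4 non-hematologic toxicity. For the drug or drugs to which it is attributed, "dose interruption of that particular drug(s) is mandatory". For grade 3, the section adds that "the patient must have recovered to grade" 1 or less before the next course. For grade 4, a later course also needs the Principal Investigator's approval and evidence of benefit.

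**The concern.** Section 5.2 conditions bridging on counts alone, yet one of its own reasons for a hold has nothing to do with counts. A patient can have good counts and an unresolved severe non-hematologic event attributed to INCB018424. For that patient one section expressly allows the drug to go on at a stated dose, and the other requires it to be interrupted. Neither section refers to the other.

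At stake is whether a patient with severe drug-attributed toxicity stays on that drug during the wait. Safety of the combination is the trial's secondary objective, so the rule for handling severe toxicity should have one reading.

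**Working it through.** The question is one of rule logic, so the check sets the two sections against each other. The plan states no figure to reproduce on this point.

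**Step 1: who can reach each bridging branch.** A patient on hold fails at least one of the three start conditions. The 5 mg BID thresholds (ANC at least 1,000, platelets above 50) are the same as conditions 1 and 2. A held patient who meets them therefore fails condition 3, the unresolved drug-related grade 3-4 event.

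An enumeration confirms this. It used 9 ANC values (400 to 2,000), 11 platelet values (30 to 150) and 3 event states, which gives 9 × 11 × 3 = 297 combinations. Of these, 24 may start a cycle and 273 are on hold:

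| Branch met while on hold | No unresolved event | Hematologic event | Non-hematologic event | Total |
|---|---|---|---|---|
| 5 mg BID | 0 | 24 | 24 | 48 |
| 5 mg QD only | 39 | 39 | 39 | 117 |
| Neither | 36 | 36 | 36 | 108 |

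These are counts of rule combinations, not patient frequencies. They show that the BID branch is reached only through condition 3, and that the QD branch can also be met with an unresolved non-hematologic event.

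**Step 2: where the two sections agree and where they do not.**

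| Unresolved grade 3-4 event | Section 5.2, counts met | Section 5.1 mandatory interruption of INCB018424 | Result |
|---|---|---|---|
| Hematologic | Permits INCB018424 | Does not apply | Consistent |
| Non-hematologic, lenalidomide alone | Permits INCB018424 | Does not apply (interruption is drug-specific) | Consistent |
| Non-hematologic, INCB018424 alone or with lenalidomide | Permits INCB018424 | Applies | Contradiction |

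The first row is a real use of the BID branch: Section 5.2 itself foresees a delay in which platelets stay above 50 but at or below 75 × 10⁹/L.

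**Step 3: whether the wording of 5.2 removes the third row.** It could be said that a drug already interrupted cannot continue. But Section 5.2 also covers toxicity first met on the scheduled Day 1, and Section 5.0 gives INCB018424 continuously through the 28 days. Such a patient can be on the drug when the hold begins.

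**Step 4: size of the exposure.** Sections 5.0 and 5.2 allow a hold of up to 8 weeks, with a documented Principal Investigator exception in 5.2. At 5 mg BID the daily dose is 2 × 5 = 10 mg. Against the dose table in Section 5.1:

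- Level 0: 2 × 15 = 30 mg; 10/30 = 33%.
- Levels -1 and -2: 2 × 10 = 20 mg; 10/20 = 50%.
- Level -3: 2 × 5 = 10 mg; 10/10 = 100%.

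At level -3 the permitted bridging dose is the patient's full dose, so it cannot be read as an interruption.

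**The case against.** The strongest reply is that the sections can be read together. Section 5.2 only permits dosing, while Section 5.1 mandates interruption, so withholding INCB018424 complies with both. This stands in part. A reader might infer that Section 5.2 orders a site to dose the patient, and it does not. But the permission is express and unqualified, and the text does not say that it yields to Section 5.1.

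Three further points stand and narrow the concern:

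- A reader might infer from Step 1 that the BID branch has no use outside the conflict. It does: hematologic events and events attributed to lenalidomide alone.
- A reader might infer that the Section 5.1 recovery and Principal Investigator approval conditions also conflict with bridging. They govern the next course, whereas bridging takes place before it. Condition 3 of Section 5.2 itself requires resolution to grade 1 or less.
- A reader might infer that local sites will handle the same patient differently. The outside-physician rules under Section 5.6 require the central physician investigator to discuss and approve dose changes, which limits this. Section 5.7 also requires discontinuation for events the investigator judges may cause severe or permanent harm. Neither rule settles the conflict, because the approving physician works from the same two texts.

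**Conclusion.** The contradiction is real but confined to one group: patients on hold for a drug-related grade 3-4 non-hematologic event attributed to INCB018424, alone or with lenalidomide, whose counts meet either bridging branch. The conclusion assumes that the hold arises from the three listed conditions and not from a logistical delay.

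The size is a hold of up to 8 weeks, at a permitted BID dose equal to 33% of the level 0 daily dose and 100% at level -3. How many of the planned 49 patients would be affected cannot be derived. Section 2.2 reports grade 3 or 4 events in fewer than 10% at the 15 mg BID starting dose of single-agent INCB018424. That figure is mainly myelosuppression, does not describe the combination, and does not show how many events would still be open on a scheduled Day 1.

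A reader might also infer that bridging would prolong events, push patients past the 8-week limit or distort the safety results. The documents do not support this: adverse events are recorded throughout, and Section 8.0 includes everyone who received any study drug in the safety analyses. The point is a safety clarification. It does not affect the primary endpoint or the two-stage design.

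**What to change.** Reconcile the bridging sentence in Section 5.2 with the mandatory-interruption sentence in Section 5.1. The bridging sentence should state which reasons for delay it covers and how it relates to the Section 5.1 interruption when the event is non-hematologic and attributed to INCB018424. Which rule should govern is for the sponsor's medical team to decide.

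The cost is one sentence in a protocol amendment, with no added visits, tests or patients.

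### Section 5.2 gives overlapping, unranked dosing rules for a cycle delayed about 4 weeks with platelets above 50 and up to 75 x 10^9/L, and its lenalidomide reduction has no effect from Levels +1 and 0

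*Combined protocol and SAP*

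**What the plan says.** Section 5.2 has three layers, followed by a rider.

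1. **Scheduled start.** "A new course of treatment may begin on the scheduled Day 1 of a new cycle if" three conditions hold: ANC of at least 1,000/µL, platelets above 50 x 10^9/L, and any drug-related grade 3-4 event back to grade 1 or lower.
2. **Delayed start (general rule).** If the conditions fail, the patient is checked weekly and "a new cycle will not be initiated until the toxicity has resolved as described above". After an interruption in the previous cycle or a new delay for toxicity, "then the new cycle will be started when the criteria above are met AND with at least a one-level dose reduction".
3. **Four-week rule (special rule).** "If after a 4 week delay, the platelet count remains" above 50 but not above 75, the cycle may begin with INCB018424 at 5 mg BID and "the dose of lenalidomide reduced by at least 1 dose level from the prior cycle".
4. **Rider.** If the prior cycle was at Level -2 or -3, lenalidomide has to stop and INCB018424 may go on alone.

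A further sentence in Section 5.2 allows INCB018424 at 5 mg BID during the wait when ANC is at least 1,000/µL and platelets are above 50. Section 5.1 holds the dose-level table. Section 8.0 treats a patient who stopped one of the two drugs for safety as a failure in the efficacy analysis.

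**The concern.** The special rule reads as if a count between 50 and 75 had been holding the cycle. The start conditions contain no such threshold: any count above 50 passes. The special rule therefore overlaps with the general rule for delayed cycles, and nothing states which one prevails.

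Three things are at stake. The INCB018424 dose at a given count depends on which sentence is applied. At the lower dose levels, the choice can decide whether a patient stays on both drugs, which bears on the primary endpoint. And the instruction to lower lenalidomide by a level has no effect at some levels, including the planned starting level. Section 2.2 names reversible thrombocytopenia as the basis for the INCB018424 maximum tolerated doses, so low platelet counts are a situation in which the dosing text needs to be clear.

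**Working it through.** The plan states no figure to reproduce. The check is a trace of the Section 5.2 rules through the Section 5.1 table. The table is read as INCB018424 in mg BID and lenalidomide in mg, which matches the planned doses in Section 5.0 at Level 0.

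**Step 1: when does each rule apply?** Platelets are in 10^9/L; other conditions are met unless stated.

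- 60 on scheduled Day 1, no interruption in the prior cycle: the cycle starts. The special rule is not reached.
- 40 on Day 1, 60 at week 1: the general rule applies. The special rule is not reached.
- 50 or below through week 3, 60 at week 4: both rules apply.
- 60 throughout, held for ANC or an adverse event that has resolved by week 4: both rules apply.
- 60 throughout, ANC still below 1,000/µL at week 4: the general rule keeps the cycle on hold; the special rule says nothing about ANC.
- Held only because platelets sit between 50 and 75: impossible, since a count above 50 meets the start condition and a platelet-only hold ends at the first weekly count above 50.

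The last line is why *remains* and the upper bound of 75 fit no threshold in force. The figure 75 appears in no other start or dose rule in Sections 5.1 and 5.2. The waiting-dose sentence has a similar difficulty: a patient with ANC of at least 1,000/µL and platelets above 50 already meets both blood-count conditions, so only an unresolved adverse event could explain the wait.

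**Step 2: what dose follows at week 4 with a count of 60?** The general rule is taken at its minimum, one level down.

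| Prior level | General rule: INCB018424 / lenalidomide | Special rule and rider: INCB018424 / lenalidomide | INCB018424 difference (mg BID) |
|---|---|---|---|
| +3 (25 / 15) | 20 / 10 | 5 / 10 or lower | 20 - 5 = 15 |
| +2 (20 / 10) | 20 / 5 | 5 / 5 or lower | 20 - 5 = 15 |
| +1 (20 / 5) | 15 / 5 | 5 / 5 if one table row down | 15 - 5 = 10 |
| 0 (15 / 5) | 10 / 5 | 5 / 5 if one table row down | 10 - 5 = 5 |
| -1 (10 / 5) | 10 / 5 every other day | 5 / 5 every other day or lower | 10 - 5 = 5 |
| -2 (10 / 5 every other day) | 5 / 5 every other day | INCB018424 alone; lenalidomide stops | 0 if 5 mg BID is used |
| -3 (5 / 5 every other day) | no lower row in the table | INCB018424 alone; lenalidomide stops | not defined |

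**Step 3: the lenalidomide reduction.** Lenalidomide is 5 mg at +1, 0 and -1. One row down from +1 or from 0 therefore changes nothing. If a level instead means a step in lenalidomide itself, the step from 5 mg daily is to every-other-day dosing. Section 5.2 does not say which is meant.

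**Step 4: link to the primary endpoint.** From Level -2, the general rule permits both drugs at Level -3; the rider requires lenalidomide to stop. It is also unclear whether the rider covers every delayed cycle or only the four-week case. If the stop counts as one for safety, Section 8.0 makes the patient a failure. The decision limits are 10 versus 11 responders of 31 and 21 versus 22 of 49, so one reclassified patient changes the decision only when the total lies at a limit.

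**The case against.** The best reply is that the special rule is a narrower case of the general one. The general rule sets a minimum reduction, the special rule is permissive, and from Level 0 a dose of 5 mg BID satisfies both. A cycle can also be held for ANC, for an adverse event, or for platelets earlier at 50 or below, so a count of 50 to 75 at week 4 need not have caused the delay. Under Section 5.6, changes made by an outside physician need approval from the investigator at the centre or a representative, and Section 5.1 allows other modifications with documented approval.

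Much of this stands. The two dosing rules are not mutually exclusive, and central approval limits variation. But it does not settle which rule governs, what ANC is required at week 4, or how far the rider reaches. At Level -2, one text permits continuing lenalidomide and the other requires stopping it.

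A reader might also infer more than the documents support:

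- *That the scheduled-start rule and the four-week rule collide at every cycle start with platelets of 50 to 75.* They do not: the special rule needs a 4-week delay first.
- *That the repeated lenalidomide dose at -2 and -3 makes the four-week reduction empty there too.* The rider deals with both levels by stopping the drug.
- *That the grade 3-4 thrombocytopenia rates in Section 2.3 (13% to 19%) show how often this happens.* They come from lenalidomide alone or with prednisone, and do not measure counts of 50 to 75 after a 4-week delay on this combination.

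**Conclusion.** The point holds as an internal inconsistency confined to cycles delayed about 4 weeks with platelets above 50 and up to 75 x 10^9/L, together with a lenalidomide reduction that is empty for a one-row step from +1 or 0. In the affected cycles the INCB018424 dose can differ by 5 to 15 mg BID from prior Levels +3 to -1. From Level -2 the choice of rule can decide whether a patient stays on both drugs and so can alter the primary outcome.

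The dose differences assume the general rule is applied at its one-level minimum. The endpoint effect assumes that the required stop is classed as a safety stop and that the patient would otherwise have been a responder. The number of patients affected cannot be determined from the documents. No view is taken on which threshold or dose is right. The point is more than editorial because it bears on dose and possibly on outcome, and it should be corrected.

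**What to change.** Reconcile five provisions: the platelet start threshold, the waiting-dose sentence, the four-week rule, the scope of the lenalidomide stop, and the Section 5.1 table. After the change:

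- one rule should apply to each combination of platelet range and delay length, with precedence stated;
- the ANC and adverse-event conditions for a start at week 4 should be explicit;
- the text should say whether the lenalidomide stop applies to every delayed cycle or only to the four-week case;
- a lenalidomide level reduction should have a defined meaning at every level;
- Section 8.0 should say whether a stop required by this rule counts as a safety stop.

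The clinical team decides the content. The cost is a wording amendment, with no extra patients or data.
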